#### 7.3.2 STOPPING RULES (CRITERIA FOR PAUSING OF STUDY)

If any of the following situations occur then further enrollment and Study Treatments will be halted immediately until a thorough investigation has been conducted by the Medical Monitor and PI, the DSMB, and the IRB/EC (if applicable):

- One third or more subjects experience an AESI assessed as related to Study Treatment;
- Any subject experiences an SAE (or potentially life threatening AE) or death assessed as related to Study Treatment;
- Three or more subjects experience the same grade 3 or 4 adverse event, assessed as related to Study Treatment;
- In the event of two identical, unexpected, Grade 4 toxicities, assessed as related to Study Treatment;

Upon conclusion, the sponsor or designee will notify all Investigators and IRBs/EC (if required) regarding the outcome of any investigation stemming from a Study Pause.

Guidelines for assessing relatedness are detailed in [Section 7.1.8](#).

## 7.4 ADVERSE EXPERIENCE REPORTING

To assure the safety of the subjects, information about all AEs (see [Section 7.1](#)), whether volunteered by the subject, discovered by Investigator or study staff questioning, or detected through physical examination, laboratory test or other means, will be collected and recorded in the subject's source documents and followed as appropriate.

### 7.4.1 TRIAL REPORTING PERIOD OF ADVERSE EVENTS

All solicited and unsolicited adverse events will be collected throughout the study and recorded in the electronic data capture (EDC) system.

### 7.4.2 TRIAL REPORTING PERIOD OF SERIOUS ADVERSE EVENTS

The reporting period for SAEs (without regard to causality or relationship) is comprised of the period following the signing of the informed consent form until the end of the study. Each AE will be assessed to determine whether it meets serious criteria. If the AE is considered serious, the Investigator should record this event in the EDC system and report the event to the Sponsor within 24 hours of becoming aware of the event. The Investigator may also directly report this event to the Ethics Committee according to its standard operating procedures. Expectedness of SAEs will be determined by the Sponsor using reference safety information specified in the Investigator's Brochure and protocol.

An event may qualify for expedited reporting to regulatory authorities if it is an SAE, unexpected per reference safety information and considered related following the guidelines in [Section 7.1.5](#) (Suspected Unexpected Serious Adverse Reaction, SUSAR) and [7.1.6](#) (Unanticipated [serious] adverse device effect) in line with relevant legislation. All Investigators will receive a safety letter notifying them of relevant SUSAR reports. The Investigator should notify the Institutional Review Board (IRB)/Ethics Committee (EC) as soon as is practical, of serious events in writing where this is required by local regulatory authorities, and in accordance with the local institutional policy.

At any time after completion of the SAE reporting period, if an Investigator becomes aware of an SAE that is suspected by the Investigator to be related to the study drug, the event will be reported to the Sponsor or its designee. If the Investigator becomes aware of an SAE in a study subject after the last scheduled follow-up visit, and considers the event related to prior Study Treatment, the Investigator will report it to the Sponsor or the appropriate designee.

### 7.4.3 NOTIFICATION OF SERIOUS ADVERSE EVENTS

In accordance with local regulations, the Sponsor shall notify the appropriate regulatory authorities, and all participating Investigators in a written safety report of any adverse experience associated with the use of the product that is both serious and unexpected and any significant new safety information that might materially influence the benefit-risk assessment of a medicinal product, sufficient to consider changes in product administration or overall conduct of a clinical investigation. The Sponsor will notify regulatory agencies within the time frame specified by local requirements but no later than 10 working days for UADE, 7 days for a fatal or life-threatening SUSAR and 15 days for all other SUSARS (see [Section 7.1.5](#) and [7.1.6](#)).

### 7.4.4 REPORTING OF DEVICE RELATED COMPLAINTS

A product complaint (or device deficiency) involves any written, electronic, or oral communication that alleges deficiencies related to the identity, quality, durability,

reliability, safety, effectiveness, or performance of a device such as malfunction, misuse or use error and inadequate labeling. A malfunction is defined as the failure of a device to meet its performance specifications or otherwise perform as intended. The intended performance of a device refers to the intended use for which the device is labeled. All product complaints that meet this definition must be reported to the sponsor within 10 days of discovery. Any product complaint that involves an AE or SAE must be also be reported per [Section 7.4.1](#) and [Section 7.4.2](#).

Any problems experienced including potential malfunctions of the device, error messages displayed on the device screen following treatment or errors that occur during the treatment procedure must be reported to the Sponsor or designee immediately for evaluation.

All complaints must be sent to [[contact]](mailto:[contact]). Additional instructions on complaint reporting to be provided separately.

## 7.5 TRIAL DISCONTINUATION

Inovio Pharmaceuticals reserves the right to discontinue the study at this site or at multiple sites for safety or administrative reasons at any time. In particular, a site that does not recruit at a reasonable rate may be discontinued. Should the study be terminated and/or the site closed for whatever reason, all non-source documentation and study product pertaining to the study must be returned to Inovio Pharmaceuticals or its representative.

The study may be discontinued at any time by an IRB, Inovio Pharmaceuticals Inc., the FDA or other government agencies as part of their duties to ensure that research subjects are protected.

## 8. STATISTICAL ANALYSIS PLAN

### 8.1 GENERAL CONSIDERATIONS

The statistical analysis of the data will be performed by Inovio Pharmaceuticals or its representative.

This is a two-arm, multi-center, open-label randomized clinical trial of VGX-3100 and VGX-3100 with imiquimod, in subjects with a histologic diagnosis vulvar HSIL and confirmed vulvar infection with HPV types 16 and/or 18. The study's primary endpoint is binary: regression of vulvar HSIL and viral clearance of HPV-16 and/or HPV-18 from vulvar tissue based on tissue collected at Week 48. The primary hypothesis is that each of the treatment arms will result in regression of HSIL and clearance. Secondary efficacy analyses pertain to regression, clearance of HPV-16 and/or HPV-18 infection, regression to normal, non-progression, and anatomic extent. Other secondary analyses concern safety and humoral and cellular immunological measures. Exploratory efficacy analyses concern extended dosing with respect to regression, clearance, and anatomic extent, clearance outside of the vulva, and effect of HLA type on efficacy. Other exploratory analyses pertain to tissue immunological measures and patient-reported outcomes.

### 8.2 RANDOMIZATION AND BLINDING

Subjects will be randomized two to one, VGX-3100 alone: VGX-3100 in combination with topical imiquimod. Subjects will be randomized in a stratified manner according to (a)

recurrent disease at screening (0 vs. 1 or more recurrences), (b) multifocal disease (1 vs. 2 or more lesions at screening), (c) Body Mass Index (BMI) category ( $\leq 25$  vs.  $> 25$  kg/m^2), and (d) age category ( $< 45$  years vs.  $\geq 45$  years). There are no requirements for the number of subjects in each stratum. The study is open-label.

### 8.3 SAMPLE SIZE/POWER

A sample of 36 subjects will be randomized to receive either 6 mg VGX-3100 or 6 mg VGX-3100 plus imiquimod, IM followed by EP in a 2:1 ratio. This sample size provides 80% power to declare each arm superior to historical control with a one-sided 0.025 type 1 error level for each hypothesis, assuming the true proportion of subjects who achieve the primary endpoint is 20% and 28% for the respective treatment arms and 2% for the historical control, and that 90% are evaluable at Week 48 from randomization.

### 8.4 ANALYSES POPULATIONS

Analysis populations will include:

- The modified intention to treat (mITT) population includes all subjects who receive at least one dose of Study Treatment and who have the analysis endpoint of interest. Subjects in this sample will be grouped to treatment arms as randomized. Analysis of the mITT population will be primary for the analysis of efficacy in this study.
- The per-protocol (PP) population comprises subjects who receive all doses of Study Treatments and have no protocol violations and who have the analysis endpoint of interest. Subjects in this sample will be grouped to treatment arms as randomized. Analyses on the PP population will be considered supportive of the corresponding mITT population for the analysis of efficacy. Subjects excluded from the PP population will be identified and documented prior to unblinding of the study database.
- The safety analysis set includes all subjects who receive at least one dose of Study Treatment. Subjects will be analyzed as to the treatment they received.

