### 3.2.1 DEFINITION OF RESPONDER AND NON-RESPONDER

A treatment responder is defined as a subject with no histologic evidence of vulvar HSIL and no evidence of HPV-16 or HPV-18 in vulvar tissue at evaluation and who did not receive any non-study related treatment for vulvar HSIL. A treatment non-responder is a subject with histologic evidence of vulvar HSIL or vulvar carcinoma at evaluation, or a subject with evidence of HPV-16/18 at evaluation, or a subject who received non-study related treatment for vulvar HSIL. Any case of histologically confirmed progression is considered a non-responder. Progression is defined as advancement to carcinoma by histology according to the PAC.

Responder and non-responder definitions (Table 3) take into account both histopathologic regression of vulvar HSIL and virologic (HPV-16/18) clearance from tissue samples since HPV persistence is an important factor in the clinical progression of HSIL.

Table 3: Definition of Responder and Non-responder	
Responder	Non-Responder
Subject with no histologic evidence of vulvar HSIL AND Subject with no evidence of HPV-16 or HPV-18 in vulvar tissue at evaluation AND Subject who did not receive any non-study related treatment for vulvar HSIL	Subject with histologic evidence of vulvar HSIL or vulvar carcinoma at evaluation OR Subject with evidence of HPV-16 or HPV-18 in vulvar tissue at evaluation OR Subject who received non-study related treatment for vulvar HSIL

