#### **4.3.2 CRITERIA FOR WITHDRAWAL FROM THE STUDY**

All subjects who begin treatment should be encouraged to complete all phases of the study, including those who discontinue treatment. A subject may voluntarily withdraw from study participation at any time. A subject may be withdrawn at any time at the

discretion of the Investigator for any maternal obstetrical or medical complications after consultation with the medical monitor.

Subjects who become ineligible to continue on study based on no longer meeting exclusion criteria should be discontinued from study treatment, managed per routine standard of care and should continue on study without further biopsy.

Subjects who are withdrawn from study participation after starting treatment will not be replaced. Reasons for study withdrawal will be recorded in the electronic case report form (eCRF) and the subject's source document.

Should a subject fail to attend the clinic for a required study visit, the site should attempt to contact the subject and reschedule the missed visit as soon as possible. The site should also counsel the subject on the importance of maintaining the assigned visit schedule for follow-up and treatment of VIN, and ascertain whether or not the subject wishes to and/or should continue in the study based on previous noncompliance. In cases where the subject does not return for the rescheduled visit or cannot be reached to reschedule the missed visit, the site should make every effort to regain contact with the subject (3 telephone calls to the subject should be made and if that fails, then a certified letter is sent to the subject's last known mailing address) so that they can be considered withdrawn from the study for disposition purposes. These contact attempts should be documented in the subject's medical record. Should the subject continue to be unreachable, then and only then will she be considered to have withdrawn from the study with a primary reason of "Lost to Follow-up". For all other subjects withdrawing from the study, an alternative reason for discontinuation should be recorded in the eCRF.

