### **8.11.6 MISSING VALUES**

Missing data will not be imputed or replaced, and calculations will be done on reported values.

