**Figure 4: Evaluation process at Week 100**

In the event of worsening disease at any time (i.e., Subgroup E – any increase in lesion area from baseline or worsening to cancer), the subject will receive surgical treatment per the Investigator's judgment and will continue on study through Week 100 with vulvoscopy, but without further study treatment or biopsy. If at any time in the study carcinoma is discovered, subjects will receive surgical treatment, and be discontinued from study treatment. The event will be reported as an SAE per section 7.1.4. If wide excision is required, the sample obtained will be sent to the PAC for evaluation.

Definition of Responder and Non-responder: Responder and non-responder definitions (Table 3) take into account both histopathologic regression of vulvar HSIL and virologic (HPV-16/18) clearance from tissue samples since HPV persistence is an important factor in the clinical progression of HSIL. A treatment responder is defined as a subject with no histologic evidence of vulvar HSIL and no evidence of HPV-16 or HPV-18 in vulvar tissue at evaluation and who did not receive any non-study related treatment for vulvar HSIL. A treatment non-responder is a subject with histologic evidence of vulvar HSIL or vulvar carcinoma at evaluation, or a subject with evidence of HPV-16/18 at evaluation, or a subject who received non-study related treatment for vulvar HSIL. Any case of histologically confirmed progression from HSIL to carcinoma is considered a non-responder.

Safety Assessment: Subjects will be monitored for:

- 1) Local and systemic events for 7 days following each VGX-3100 dose as noted in the Participant Diary
- 2) All adverse events including SAEs, SUSARs, UADEs, and other unexpected AEs for the duration of the study.

All subjects will be followed for 100 weeks.

Data Safety & Monitoring Board (DSMB): The DSMB will meet quarterly to review safety data and tissue regression and viral clearance results. The DSMB will be charged with advising the Sponsor if there appears to be a safety issue. No formal interim analysis is planned. The following stopping rules will be applied:

- If at any time during the study one-third (1/3) or more of the subjects experience an Adverse Event of Special Interest (AESI), further enrollment and study treatment will be halted immediately until a thorough investigation has been conducted by the Medical Monitor, Principal Investigator (PI) for the trial, and the DSMB.

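### The primary efficacy set leaves out dosed women who have no Week 48 endpoint, so some failures can leave the denominator and inflate the reported response rate

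*Protocol*

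**What the plan says.** Section 8.4 builds the mITT set from women "who receive at least one dose of Study Treatment and who have the analysis endpoint of interest" and adds: "Analysis of the mITT population will be primary for the analysis of efficacy in this study". Section 8.11.6 states: "Missing data will not be imputed or replaced, and calculations will be done on reported values". Section 8.1 makes the primary endpoint binary and "based on tissue collected at Week 48"; Section 8.9 opens the window for that visit 14 days earlier.

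Other passages decide who will have that tissue:

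- The synopsis text under Figure 4 says that a woman whose disease worsens at any time (Subgroup E: lesion area above baseline, or cancer) "will continue on study through Week 100 with vulvoscopy, but without further study treatment or biopsy". Section 3.2 says the same without the words on timing. Surgery in this group is left to the investigator's judgment.
- Section 4.3.2 says that women who become ineligible "should be discontinued from study treatment, managed per routine standard of care and should continue on study without further biopsy".
- The Schedule of Events (Table 1) shows the Week 48 biopsy with no exemption for worsening women; its biopsy footnote names subgroups only for Weeks 74 and 96.

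Table 3 in Section 3.2.1 lists among the non-responders a "subject who received non-study related treatment for vulvar HSIL", and the text beside it adds any histologically confirmed progression to carcinoma. Secondary endpoints 2 to 4 (regression, clearance, regression to normal) have no matching clause on treatment.

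For the per-protocol set, Section 8.4 says: "Subjects excluded from the PP population will be identified and documented prior to unblinding of the study database".

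The latest Section 8 available is that of version 2.0. The version 2.1 summary of changes lists edits to Sections 8.3 and 8.8 but none to 8.4 or 8.11.6.

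**The concern.** A set that requires an observed endpoint, together with a ban on imputation, is an observed-case analysis. That does least harm when missing results are unrelated to outcome. Here part of the missingness can follow from outcome, because the text stops biopsy in women who worsen, and lesion area is measured at Weeks 4, 12 and 27, before the primary biopsy.

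Three kinds of dosed women are left unclear:

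1. Women who worsen before Week 48 and are neither treated nor biopsied. Nothing classifies them, so they leave the denominator.
2. Women who withdraw or are lost before Week 48. Nothing classifies them either.
3. Women whom Table 3 calls non-responders but who have no Week 48 tissue. Section 8.4 does not say whether they have the endpoint, so two analysts could count them differently. For secondary endpoints 2 to 4 they may be absent altogether, and the composite and its components would then rest on different denominators.

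Each arm is compared with a fixed historical 2%, so no concurrent control shares any inflation. What is at stake is the reported response rate, its confidence interval and the comparability of the primary endpoint with its components.

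**Working it through.** **Inputs.** Null rate 2%, exact test at one-sided 0.025 in each arm (Sections 8.3 and 8.9). Assumed response 20% and 28%, 90% evaluable at Week 48, stated power 80% (Section 8.3). Arms of 24 and 12 (Section 3).

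**1. The plan's own power.** The critical count r is the smallest r with P(X ≥ r | n, 0.02) < 0.025. This gives r = 3 for every n from 13 to 31 and r = 2 for every n from 2 to 12. Evaluable numbers are 0.9 × 24 = 21.6 and 0.9 × 12 = 10.8.

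- VGX-3100 alone: P(X ≥ 3 | 21, 0.20) = 0.8213; P(X ≥ 3 | 22, 0.20) = 0.8455.
- VGX-3100 plus imiquimod: P(X ≥ 2 | 10, 0.28) = 0.8170; P(X ≥ 2 | 11, 0.28) = 0.8577.

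The stated 80% is reproduced as a floor in both arms.

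**2. Effect on the reported rate.** The documents do not say how many women would lack Week 48 tissue because they failed; the only figure is 10% non-evaluable. Assume that a share d of failures drops and that no responder does. The apparent rate is p / [p + (1 − p)(1 − d)].

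| d | True 20% | True 28% |
|---|---|---|
| 10% | 0.20/0.92 = 21.7% | 0.28/0.928 = 30.2% |
| 20% | 0.20/0.84 = 23.8% | 0.28/0.856 = 32.7% |
| 30% | 0.20/0.76 = 26.3% | 0.28/0.784 = 35.7% |

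Example with exact limits: 5/24 = 20.8% (95% CI 7.1 to 42.2). If three of the 19 failures drop, this becomes 5/21 = 23.8% (8.2 to 47.2).

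**3. Effect on the test.** The critical counts do not move over the plausible sample sizes, so the decisions match: 3/24 (p = 0.0118) and 3/22 (0.0093) both pass; 2/24 (0.083) and 2/21 (0.065) both fail; 2/12 (0.0231) and 2/10 (0.0162) both pass. With a true all-dosed rate of 2% and only failures dropping, type I error is:

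| Share of failures dropped | 24-woman arm | 12-woman arm |
|---|---|---|
| 10% | 0.0118 | 0.0231 |
| 20% | 0.0119 | 0.0231 |
| 30% | 0.0128 | 0.0231 |
| 40% | 0.0204 | 0.0231 |
| 50% | 0.0413 | 0.0232 |

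The larger arm exceeds 0.025 only when about half of its failures are lost, because r falls to 2 once 12 or fewer women are evaluable.

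**4. Power if all dosed women are kept.** Counting the 10% non-evaluable as failures gives success probabilities of 0.9 × 0.20 = 0.18 and 0.9 × 0.28 = 0.252. Then P(X ≥ 3 | 24, 0.18) = 83.3% and P(X ≥ 2 | 12, 0.252) = 84.5%. The present rule, averaged over a binomial number of evaluable women at 90%, gives the same 83.3% and 84.5%.

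**The case against.** The strongest reply is that the main group of failures is already handled. Table 3, and the footnote to the primary endpoint in the synopsis, make any woman given non-study treatment for vulvar HSIL a non-responder with no tissue needed, and the summary of changes says this wording was meant to cover surgery. Confirmed carcinoma is also a non-response. A reader might infer that every woman who worsens leaves the denominator; the documents do not support that. What stands is narrower: Section 8.4 is not reconciled with Table 3 for these women, and no rule covers those who worsen untreated and unbiopsied, withdraw or are lost.

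Second, it is not settled that worsening women lose the Week 48 biopsy. Table 1 shows no exemption, and Table 7 lets a woman with HSIL on an unscheduled biopsy continue her scheduled visits. That is fair; the passages conflict and must be reconciled. Worsening first found at Week 48 comes with the primary biopsy and does no harm.

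Third, a reader might infer that the test against 2% is biased. At the planned sizes it is essentially unaffected, as the working shows.

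Fourth, a reader might infer that measurement noise in three area readings would push most women with stable lesions into the worsening group. The documents give no measurement error and do not say that one higher reading automatically ends biopsies, so no such figure can be supported.

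Finally, ineligibility, withdrawal and loss are not always failure. This stands, and it is why the percentages above are conditional on an assumption. The per-protocol wording is a small matter, since that analysis is only supportive and the pathologists read masked.

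**Conclusion.** The concern holds as a defect in the primary denominator. As written, the primary set depends on having an endpoint that some failing women may not have, and the text does not say how Table 3 non-responders without tissue are counted. A separate SAP would not merely be filling a gap here, because the protocol itself fixes both the set and the missing-data rule.

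The harm is to estimation: roughly 2 to 6 percentage points on a true 20% and 2 to 8 on a true 28%, if 10% to 30% of failures and no responders drop. That range is an assumption. The conclusion of superiority over 2% is not materially at risk unless about half of the failures in the larger arm are lost.

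**What to change.** In Sections 8.4 and 8.11.6:

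- Define the primary efficacy set as all randomised women who received at least one dose.
- Count as a non-responder for the primary endpoint any woman without an evaluable Week 48 tissue result, and any woman who is already a non-responder under Table 3.
- State the denominators for the component endpoints (regression, clearance) on the same basis.
- Report the observed-case rate as a sensitivity analysis.

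Reconcile the worsening-disease text in the synopsis and Section 3.2 with Table 1, so that it is clear whether the Week 48 biopsy applies to these women.

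As a minor edit, replace the reference to unblinding in the per-protocol definition. The study is open-label, so a workable rule is that exclusions are fixed before Week 48 pathology and PCR results reach those deciding them.

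The cost is wording and a slightly lower point estimate. No extra women are needed: at 24 and 12 dosed the critical counts stay at 3 and 2 and the stated 80% power holds. One caution: if 13 women were dosed in the combination arm, its critical count would become 3.
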